6.4.7 Week 12 (Day 85)

The following procedures will be performed at Week 12 (Day 85):

- Record concomitant medications.
- Obtain body weight (prior to study drug administration).
- Perform complete physical examination (prior to study drug administration).
- Record vital signs (systolic and diastolic blood pressure, pulse rate, and body temperature) (prior to study drug administration).
- Collect blood samples for blood biochemistry, hematology, and coagulation for analysis by the local laboratory (Japan sites) and central laboratory (US sites) (prior to study drug administration).
- Collect urine sample for urinalysis by the local laboratory (Japan sites) and central laboratory (US sites) (prior to study drug administration) (if possible).
- Collect blood sample for CMV DNA analysis by the central laboratory (prior to study drug administration).
- Collect blood samples for CMV DNA analysis or CMV antigenemia testing for analysis by the local laboratory (prior to study drug administration).
- Collect blood sample for serum NPC-21 concentration measurement (within 2 hours prior to study drug administration and at 2 hours [\pm 30 minutes] following the beginning of the infusion).
- Collect blood sample for anti-NPC-21 antibody measurement (prior to study drug administration).
- Perform 12-lead ECG (prior to study drug administration).
- Administer NPC-21 (at a dose of 6 or 12 mg/kg of actual body weight [at Screening]) or placebo via an approximately 60-minute intravenous infusion at a constant rate of 5 mL/minute.

Note: Patients will be asked to remain at rest in the supine position, in principle, during study drug administration and should remain resting, in principle, from the end of study drug administration until the tests scheduled within 1 hour after study drug administration.

Note: If an adverse event occurs during study drug administration and the Investigator deems it necessary, deceleration, suspension, or resumption of study drug administration is allowed (see Section 5.5.3 for details).

- Record adverse events.

6.4.8 Weeks 13, 14, and 15 (Days 92, 99, and 106)

The following procedures will be performed at Weeks 13, 14, and 15 (Days 92, 99, and 106):

- Record concomitant medications.
- Record vital signs (systolic and diastolic blood pressure, pulse rate, and body temperature).
- Collect blood samples for blood biochemistry, hematology, and coagulation for analysis by the local laboratory (Japan sites) and central laboratory (US sites) (Week 14 only).
- Collect urine sample for urinalysis by the local laboratory (Japan sites) and central laboratory (US sites) (Week 14 only) (if possible).
- Collect blood sample for CMV DNA analysis by the central laboratory.
- Collect blood samples for CMV DNA analysis or CMV antigenemia testing for analysis by the local laboratory.
- Collect blood sample for serum NPC-21 concentration measurement (Week 14 only).
- Record adverse events.

6.4.9 Week 16 (Day 113)

The following procedures will be performed at Week 16 (Day 113):

- Record concomitant medications.
- Obtain body weight.
- Perform complete physical examination.
- Record vital signs (systolic and diastolic blood pressure, pulse rate, and body temperature).
- Collect blood samples for blood biochemistry, hematology, and coagulation for analysis by the local laboratory (Japan sites) and central laboratory (US sites).
- Collect urine sample for urinalysis by the local laboratory (Japan sites) and central laboratory (US sites) (if possible).
- Collect blood sample for CMV DNA analysis by the central laboratory.
- Collect blood samples for CMV DNA analysis or CMV antigenemia testing for analysis by the local laboratory.
- Collect blood sample for serum NPC-21 concentration measurement.
- Collect blood sample for anti-NPC-21 antibody measurement.
- Collect blood samples that will be stored for screening for resistant strains analysis.
- Perform 12-lead ECG.
- Perform EQ-5D-5L.
- Record adverse events.

6.5 Observation Period (Day 114 to Day 197)

During the 12-week Observation Period, visits and procedures will occur within ± 3 days of the scheduled time. After first study drug administration, patients who develop detectable CMV disease (CMV syndrome [see Appendix C for definition of CMV syndrome] or tissue-invasive CMV disease [see Appendix D for definitions of CMV disease]) or CMV viremia (defined as the detection of ≥ 250 IU/mL in plasma measured by PCR analysis in central laboratory or meets the local criteria for CMV viremia measured by PCR analysis or antigenemia testing) can enter the Rescue Phase of the study and be treated by anti-CMV agents per local standard of care until the patient is negative for CMV viremia, has recovered from CMV disease, or up to Week 28, whichever comes first. When this rescue therapy is completed, the Rescue Phase is terminated at least 4 Study Weeks after the last study drug administration and all Week 28 procedures will be performed as per Section 6.7 Early Termination Visit and Withdrawal Procedures. See Section 6.6 for a list of procedures to be performed upon entering the Rescue Phase.

Note: Home healthcare services (United States only) may be utilized at Weeks 17, 18, 19, 20, 21, 22, 23, 24, 26, and 28.

Note: During the 12-week Observation Period, visits at Weeks 17, 19, 21, and 23 may be missed due to unavoidable circumstances (eg, holidays, natural disasters). However, every attempt should be made to ensure a visit occurs. In this case, study staff will make contact with the patient to evaluate their condition, eg, review concomitant medications, any new adverse events since the last visit.

6.5.1 Weeks 17, 18, and 19 (Days 120, 127, and 134)

The following procedures will be performed at Weeks 17, 18, and 19 (Days 120, 127, and 134):

Note: During the 12-week Observation Period, visits at Weeks 17 and 19 may be missed due to unavoidable circumstances (eg, holidays, natural disasters). However, every attempt should be made to ensure a visit occurs. In this case, study staff will make contact with the patient to evaluate their condition, eg, review concomitant medications, any new adverse events since the last visit.

- Record concomitant medications.
- Record vital signs (systolic and diastolic blood pressure, pulse rate, and body temperature).
- Collect blood sample for CMV DNA analysis by the central laboratory.
- Collect blood samples for CMV DNA analysis or CMV antigenemia testing for analysis by the local laboratory.

Note: It is not necessary to collect blood samples for the local laboratory in the case home healthcare services (United States only) are utilized.

- Record adverse events.

6.5.2 Week 20 (Day 141)

The following procedures will be performed at Week 20 (Day 141):

- Record concomitant medications.
- Obtain body weight.

- Perform complete physical examination.
- Record vital signs (systolic and diastolic blood pressure, pulse rate, and body temperature).
- Collect blood samples for blood biochemistry, hematology, and coagulation for analysis by the local laboratory (Japan sites) and central laboratory (US sites).
- Collect urine sample for urinalysis by the local laboratory (Japan sites) and central laboratory (US sites) (if possible).
- Collect blood sample for CMV DNA analysis by the central laboratory.
- Collect blood samples for CMV DNA analysis or CMV antigenemia testing for analysis by the local laboratory.
- Collect blood sample for serum NPC-21 concentration measurement.
- Perform 12-lead ECG.
- Record adverse events.

6.5.3 Weeks 21, 22, and 23 (Days 148, 155, and 162)

The following procedures will be performed at Weeks 21, 22, and 23 (Days 148, 155, and 162):

Note: During the 12-week Observation Period, visits at Weeks 21 and 23 may be missed due to unavoidable circumstances (eg, holidays, natural disasters). However, every attempt should be made to ensure a visit occurs. In this case, study staff will make contact with the patient to evaluate their condition, eg, review concomitant medications, any new adverse events since the last visit.

- Record concomitant medications.
- Record vital signs (systolic and diastolic blood pressure, pulse rate, and body temperature).
- Collect blood sample for CMV DNA analysis by the central laboratory.
- Collect blood samples for CMV DNA analysis or CMV antigenemia testing for analysis by the local laboratory.

Note: It is not necessary to collect blood samples for the local laboratory in the case home healthcare services (United States only) are utilized.

- Record adverse events.

6.5.4 Week 24 (Day 169)

The following procedures will be performed at Week 24 (Day 169):

- Record concomitant medications.
- Obtain body weight.
- Perform complete physical examination.
- Record vital signs (systolic and diastolic blood pressure, pulse rate, and body temperature).
- Collect blood samples for blood biochemistry, hematology, and coagulation for analysis by the local laboratory (Japan sites) and central laboratory (US sites).

- Collect urine sample for urinalysis by the local laboratory (Japan sites) and central laboratory (US sites) (if possible).
- Collect blood sample for CMV DNA analysis by the central laboratory.
- Collect blood samples for CMV DNA analysis or CMV antigenemia testing for analysis by the local laboratory.
- Collect blood sample for serum NPC-21 concentration measurement.
- Perform 12-lead ECG.
- Record adverse events.

6.5.5 Week 26 (Day 183)

The following procedures will be performed at Week 26 (Day 183):

- Record concomitant medications.
- Record vital signs (systolic and diastolic blood pressure, pulse rate, and body temperature).
- Collect blood sample for CMV DNA analysis by the central laboratory.
- Collect blood samples for CMV DNA analysis or CMV antigenemia testing for analysis by the local laboratory.

Note: It is not necessary to collect blood samples for the local laboratory in the case home healthcare services (United States only) are utilized.

- Record adverse events.

6.5.6 Week 28 (Day 197)

The following procedures will be performed at Week 28 (Day 197):

- Record concomitant medications.
- Obtain body weight.
- Perform complete physical examination.
- Record vital signs (systolic and diastolic blood pressure, pulse rate, and body temperature).
- Perform urine or serum pregnancy test for females of childbearing potential only.
- Collect blood samples for blood biochemistry, hematology, and coagulation for analysis by the local laboratory (Japan sites) and central laboratory (US sites).
- Collect urine sample for urinalysis by the local laboratory (Japan sites) and central laboratory (US sites) (if possible).
- Collect blood sample for CMV DNA analysis by the central laboratory.
- Collect blood samples for CMV DNA analysis or CMV antigenemia testing for analysis by the local laboratory.
- Collect blood sample for serum NPC-21 concentration measurement.

- Collect blood sample for anti–NPC-21 antibody measurement.
- Collect blood samples that will be stored for screening for resistant strains analysis.
- Perform 12-lead ECG.
- Perform EQ-5D-5L.
- Record adverse events.

6.6 Rescue Phase

After first study drug administration, patients who develop detectable CMV disease (CMV syndrome [see Appendix C for definition of CMV syndrome] or tissue-invasive CMV disease [see Appendix D for definitions of CMV disease]) or CMV viremia (defined as the detection of ≥ 250 IU/mL in plasma measured by PCR analysis in central laboratory or meets the local criteria for CMV viremia measured by PCR analysis or antigenemia testing) can enter the Rescue Phase of the study and be treated by anti-CMV agents per local standard of care until the patient is negative for CMV viremia, has recovered from CMV disease, or up to Week 28, whichever comes first. When this rescue therapy is completed, the Rescue Phase is terminated at least 4 Study Weeks after the last study drug administration and all Week 28 procedures will be performed as per Section 6.7 Early Termination Visit and Withdrawal Procedures.

Note: Collection of blood samples for serum NPC-21 concentration measurement at Weeks 4, 8, and 12 during the Rescue Phase will be handled in the same manner as visits without study drug administration.

Note: If the patient is negative for CMV viremia or has recovered from CMV disease before 4 Study Weeks have passed following last study drug administration, weekly scheduled visits are not required. The Rescue Phase visits may be conducted by home healthcare services (United States only). The Rescue Phase procedures may be performed at the next scheduled visit after detecting CMV viremia or CMV disease with or without anti-CMV agents per local standard of care. Some Investigators may prescribe anti-CMV agents (eg, VGCV) in advance and instruct the patient to start taking the drug as soon as possible for safety if the disease or viremia develops. If this is the case, the Rescue Phase procedures may be performed at the next scheduled visit.

The following procedures will be performed upon entering the Rescue Phase:

- Record the rescue in IRT.
- Record concomitant medications.
- Record the date and reason for entering the Rescue Phase.
- Perform complete physical examination.
- Collect blood sample for CMV DNA analysis by the central laboratory.
- Collect blood samples that will be stored for screening for resistant strains analysis.
- Perform EQ-5D-5L.
- Record adverse events.

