4.2 Exclusion Criteria

Patients who meet any of the following criteria will be excluded from participation in the study:

1. Patients who have received a previous solid organ transplantation or HSCT.
2. Patients who receive a multi-organ transplant.
3. Patients who have CMV disease (CMV syndrome or tissue-invasive CMV disease) or CMV viremia (PCR analysis or antigenemia testing in local laboratory meets the local criteria for CMV viremia) at Screening.
4. Patients who have a positive donor-specific antibody within 90 days prior to Randomization confirmed via medical records.
5. Patients whose body weight is more than 120 kg at Screening.

Note: In case of hemodialysis patients, body weight is defined immediately after dialysis or dry weight. In case of peritoneal dialysis patients, body weight is defined after removal of dialysate or dry weight.

Note: Body weight measured within 7 days prior to pre-Randomization is permitted.

6. Patients who have received the following anti-CMV therapy within 7 days prior to Randomization and/or plan to receive the following anti-CMV therapy during the study:

- Anti-CMV agents (eg, foscarnet, GCV, VGCV, letermovir, high dose acyclovir [≥ 500 mg/m² intravenously every 8 hours, 10 mg/kg intravenously every 8 hours or 800 mg orally 4 times a day], high dose valacyclovir [1000 mg orally 3 times a day], high dose famciclovir [500 mg orally every 8 hours], or cidofovir).

Note: The use of anti-CMV agents per local standard of care during the Rescue Phase of the study is permitted.

Note: The use of anti-herpes simplex virus (HSV) and anti-varicella zoster virus (VZV) prophylaxis for at-risk patients is recommended (as long as the doses are below the one specified above).

7. Patients who have received the following therapy within 28 days prior to Randomization and/or plan to receive the following anti-CMV therapy during the study:
 - CMV hyperimmune globulin (eg, CytoGam®).
 - Intravenous immunoglobulin (IVIg).
 - Plasmapheresis (receipt prior to first study drug administration is acceptable).
8. Patients with a history of a serious drug allergy to proteins, immunoglobulins, transfusions, or vaccines or any excipient of the NPC-21 formulation.
9. Patients with severe hepatic insufficiency at Screening (eg, Child-Pugh Class C).
10. Patients with active and untreated hepatitis B virus or hepatitis C virus, as documented as part of the pre-transplant testing.

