8.2 Screening for Resistant Strains Analysis

Antiviral resistance in CMV seronegative patients will be evaluated by resistant strains genotypic analysis. Blood samples will be stored for screening for resistant strains analysis and will be collected prior to study drug administration on Day 1, at Weeks 16 and 28, and at the initiation of the Rescue Phase. Samples may be collected by home healthcare services (United States only) at non-dosing day visits. The resistant strains analysis of blood samples from patients with treatment failure will be conducted in this Phase 2 study based on analysis study protocol.

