3.1.5 Handling of Dropouts and Missing Data

In general, data will be analyzed and presented as observed and will not be imputed for the analysis of efficacy.

In case the start and end dates for AEs and concomitant medications/procedures are missing or incomplete, the missing component(s) will be assumed as the most conservative value possible. For example, AEs with missing start dates, but with stop dates either overlapping into the treatment period or missing, will be counted as treatment-emergent, taking the worst-case approach. When partial dates are present in the data, both a partial start date and/or a partial stop date will be evaluated to determine whether it can be conclusively established that the AE started prior to the start of study treatment or ended prior to the start of study treatment. If the above cannot be conclusively established based on the partial and/or present dates, then the AE will be considered as treatment-emergent. Actual data values as they appear in the original electronic case report forms (eCRFs) will be presented in the data listings.

All central CMV DNA PCR values will be used for the efficacy analyses and the local laboratory values will be listed. For the calculation of descriptive statistics of central CMV DNA results, below the lower limit of quantification (BLQ) values will be set to zero if result is reported as “< 102” with unit “IU/mL”. Missing data reported as “quality not sufficient” will not be imputed.

Changes in study visit schedules, missed or delayed visits, or patient discontinuations and the relationship to COVID-19 will be captured in the eCRFs.

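### The main sample for resistance genotyping may be drawn after antiviral treatment has begun, and the plan names no pre-treatment specimen to use instead

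*Protocol*

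**What the plan says.** Protocol Section 8.2 says that resistance will be evaluated by genotyping. The stored samples "will be collected prior to study drug administration on Day 1, at Weeks 16 and 28, and at the initiation of the Rescue Phase". Genotyping of "blood samples from patients with treatment failure will be conducted in this Phase 2 study based on analysis study protocol", a separate document that is not among those available.

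Protocol Section 6.6 puts the stored resistance sample on the list of procedures for entering the Rescue Phase, and then relaxes the timing of that whole list: "The Rescue Phase procedures may be performed at the next scheduled visit after detecting CMV viremia or CMV disease with or without anti-CMV agents". It adds that some investigators may prescribe an agent in advance and "instruct the patient to start taking the drug as soon as possible for safety if the disease or viremia develops". For those patients, "If this is the case, the Rescue Phase procedures may be performed at the next scheduled visit". Appendix A, footnote d, repeats this.

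Separate blood for central CMV PCR is drawn at every scheduled visit from Day 1 (Sections 6.4 and 6.5). The documents describe it only for CMV DNA measurement and do not say whether leftover plasma is kept.

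**The concern.** The two sections do not describe the same sample. Section 8.2 reads as a sample taken at the moment of failure. Section 6.6 allows it to be taken at a later visit, with treatment already running.

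The other stored samples are weak substitutes. Day 1 blood comes from seronegative patients, and Section 4.2 excludes "Patients who have CMV disease (CMV syndrome or tissue-invasive CMV disease) or CMV viremia" at Screening. After a successful rescue, the Week 28 procedures are done once viremia has cleared or disease has resolved. That leaves rescue entry as the main chance to genotype the virus that broke through. If antiviral treatment has already lowered the load, low-load failures may yield no genotype, and the virology variable loses patients from a group that is small to begin with.

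**Working it through.** **1. How many failures are at issue.** Inputs from Protocol Section 10.2.7 and SAP Section 2.2.4: 60% versus 30%, two-sided 0.05, power 80%, 15% early discontinuation.

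- n per arm = (1.960 + 0.842)² × (0.6×0.4 + 0.3×0.7) / 0.3² = 39.2, rounded up to 40.
- 40 / (1 − 0.15) = 47.1, rounded up to 48. The plan's figure is reproduced.
- Taking treatment failure to mean CMV disease or viremia by Week 16: 48 × 0.30 = 14.4 on 6 mg/kg and 48 × 0.60 = 28.8 on placebo, 43.2 in all. The 12 mg/kg arm adds 12 × 0.30 = 3.6 if 30% is assumed there.

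These are the patients who could be genotyped. They are not an estimate of samples lost.

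**2. How long the sample can wait.** Appendix A spaces visits 7 days apart to Week 24 and 14 days apart after that. Section 6.5 lets Weeks 17, 19, 21 and 23 be missed, which also gives 14 days. Both periods have windows of ±3 days.

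- Nominal gap: 7 or 14 days.
- Longest gap: 7 + 3 + 3 = 13 days, or 14 + 3 + 3 = 20 days.

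This is an upper bound on antiviral exposure before the sample. Time spent waiting for the PCR result shortens it.

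**3. What the wait could do to viral load.** The event threshold is 250 IU/mL centrally, or local criteria (Section 7.1). SAP Section 3.1.5 gives the central assay's lower limit: such "values will be set to zero if result is reported as" less than 102 IU/mL. The margin is log10(250/102) = 0.39. The documents give no on-treatment half-life h, so 2 to 8 days is assumed. Load at day t is V0 × 2^(−t/h), and the time to reach 102 is h × log2(V0/102).

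| Load at start (IU/mL) | h (days) | Days to 102 IU/mL | Load at day 7 (IU/mL) |
|---|---|---|---|
| 250 | 2 | 2.6 | 22 |
| 250 | 5 | 6.5 | 95 |
| 250 | 8 | 10.3 | 136 |
| 1,000 | 2 | 6.6 | 88 |
| 1,000 | 5 | 16.5 | 379 |
| 1,000 | 8 | 26.3 | 545 |
| 10,000 | 2 | 13.2 | 884 |
| 10,000 | 5 | 33.1 | 3,790 |
| 10,000 | 8 | 52.9 | 5,450 |

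A failure near the threshold can drop below quantification within one ordinary visit interval. One at 10,000 IU/mL does not in 7 days. At the 20-day extreme it would be about 10 to 1,768 IU/mL, so a long wait combined with fast decay could matter there too.

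**4. What losing genotypes costs.** If no resistant strain is seen among n genotyped failures, the one-sided 95% upper bound on the resistance rate is 1 − 0.05^(1/n). For n = 14 this is 19%. For n = 7 it is 35%. Losing half is purely illustrative.

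**The case against.** The strongest reply is that the separate analysis protocol may already set the specimen order, assay limits, target genes and the handling of on-treatment samples. That may be so. It cannot, however, recover plasma that was never kept, and the trial protocol is where collection and storage are fixed.

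Two further objections stand and shape the recommendation. Section 5.6.3 already collects start dates for all medications and dosing detail for anti-CMV agents, so no new data item is needed. A first-positive specimen near 250 IU/mL may itself be hard to genotype. If no antiviral has been started, the rescue-entry sample could carry more virus, so the first-positive specimen should not automatically take priority.

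A reader might also infer more than the documents support:

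- That rescue entry is the only informative sample. Week 16 or 28 blood holds virus if onset falls at that visit, if rescue has not cleared it, or if a viremic patient does not enter rescue, which the text makes optional. Day 1 is expected, not assured, to be negative: the exclusion rests on local criteria at a Screening that can be up to 14 days before dosing.
- That the delay would select variants resistant to the rescue drug and confuse them with failure of NPC-21. The protocol describes NPC-21 as binding AD-1 on glycoprotein B and ganciclovir as a DNA polymerase inhibitor. It names no genes to be sequenced, and nothing in it shows selection within one visit interval.
- That a usable pre-treatment specimen is already in storage. The blood is drawn, but its retention and spare volume are not stated. When an event is found between visits, the last scheduled specimen may predate detectable virus.
- That 102 IU/mL marks where genotyping fails. It is a quantification limit; no genotyping limit is given.

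**Conclusion.** The point holds as a timing conflict with a modest, avoidable cost. As written, the main informative resistance sample can be drawn up to one visit interval into antiviral treatment, and for low-load failures the virus may no longer be genotypable. The frequency is unknown. It depends on how many investigators prescribe in advance, on loads at detection, on an assumed half-life, and on an assay limit that the documents do not give. Resistance is not a primary or secondary efficacy endpoint, the SAP specifies no analysis of it, and the 48 per arm is unaffected. The change is worth making because it is cheap and the lost information cannot be recovered later.

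**What to change.** Reconcile Section 8.2 with Section 6.6 and Appendix A footnote d on when the rescue-entry resistance sample is taken, leaving rescue treatment as it is.

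In Sections 8.2 and 6.6, have the central laboratory keep leftover plasma from the scheduled CMV PCR specimen that first meets the event criterion, as an additional resistance specimen. Section 5.6.1 prohibits anti-CMV agents outside the Rescue Phase, so under the protocol's own rules a scheduled specimen drawn before rescue begins should predate them.

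For each failure, genotype the pre-antiviral specimen with the highest viral load, and fall back to the rescue-entry sample if none is usable. Use the start dates collected under Section 5.6.3 to flag each genotyped sample as before or after the first anti-CMV dose, and report the two groups separately by arm.

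The cost is protocol and laboratory-manual wording and a little freezer space, with no extra draw or visit. Leftover volume will sometimes be too small, and events found between visits may have no positive scheduled specimen. In both cases the trial is no worse off than now.
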